5.6 Evaluation During Study

- Directed history and physical examination including vital signs, body weight, and spleen and liver measurements once each cycle on cycles 2-7, then once every 3 cycles (C10, C13, C16, ...). This also includes a transfusion history for previous cycle of therapy and concomitant medication notation. Spleen and liver measurements will be obtained by the physicians or physician assistants during the clinic visit and documented in the medical record.
- CBC and differential, electrolytes (Na, K, Cl, Mg, HCO3), creatinine, BUN, glucose, total bilirubin, and SGPT every 2 weeks for 6 cycles, then CBC with differential every cycle and electrolytes (Na, K, Cl, Mg, HCO3), creatinine, BUN, glucose, total bilirubin, and SGPT every 3 cycles and as deemed appropriate while on therapy. Therapy also includes the first 3 months of ruxolitinib alone.
- ECG will be performed prior to the first cycle of pracinostat (C4), then once during cycles 5 and 6, then every 3 cycles starting with cycle 10 (specifically, ECG should be performed approximately 90 minutes post pracinostat dosing on the day of visit to MD Anderson)
- Bone marrow aspiration and biopsy after cycles 6 (+/- 10 days) and 12 (+/- 10 days), and if deemed appropriate by the investigator, every 6 cycles after cycle 12.
- Response assessment after cycle 3 and cycle 6, then every 6 cycles. Assessment may not include bone marrow biopsy on all occasions.
- Collect any unused study drug and review patient study drug dosing diary for compliance during each cycle for the first 7 cycles then every 3 cycles.
- Continuous assessment of AEs
- Myeloproliferative Neoplasm Symptom Assessment Form Total Symptom Score (MPN-SAF TSS) questionnaire during each cycle for the first 7 cycles then every 3 cycles.

Every effort will be made to adhere to the schedule of events and all protocol requirements within the +/- 10 day window. Variations in schedule of events and other protocol requirements that do not affect the rights and safety of the patient will not be considered as deviations. Such variations may include laboratory assessments completed outside of schedule, occasional missed required research samples such as PK or PD. All dose adjustments will be made according to the protocol unless discussed with the PI and do not exceed the dosages described in the protocol.

Outside Physician Participation During Treatment

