- MDACC Physician communication with the outside physician is required prior to the patient returning to the local physician. This will be documented in the patient record
- A letter to the local physician outlining the patient's participation in a clinical trial will request local physician agreement to supervise the patient's care
- Protocol required evaluations outside MDACC will be documented by telephone, fax or e-mail. Fax and/or e-mail will be dated and signed by the MDACC physician, indicating that they have reviewed it.
- Changes in drug dose and/or schedule must be discussed with and approved by the MDACC physician investigator, or their representative prior to initiation, and will be documented in the patient record.
- A copy of the informed consent, protocol abstract, and evaluation during treatment will be provided to the local physician.
- Documentation to be provided by the local physician will include drug administration records, progress notes, reports of protocol required laboratory and diagnostic studies and documentation of any hospitalizations.
- The home physician will be requested to report to the MDACC physician investigator all life threatening events within 24 hours of documented occurrence.
- Patients will return to MDACC each cycle for the first 6 cycles then every 3 cycles as long as on the study for evaluation.

The patient will be contacted by the PI and his staff 30 days after discontinuation of protocol +/-14 days to assess for AE's, unless the patient receives further MF-directed treatment.

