7.2 Expedited reporting by investigator to Helsinn Healthcare SA

Serious adverse events (SAE) are defined above. The investigator will inform Helsinn Healthcare SA of any SAE within 24 hours of being aware of the event via email and/or fax.

All pregnancies will also be reported.

The following SAEs are not subject to expedited reporting, but will be included in the annual report via the SAE log.

- a. Infection or cytopenias leading to hospitalization or prolongation of hospitalization; disease progression leading to death; life-threatening AE, hospitalization or prolongation of hospitalization, or disability.

Adverse events will be documented in the medical record and entered into the case report form. PDMS/CORe will be used as the electronic case report form for this protocol. Investigator or physician designee is responsible for verifying and providing source documentation for all adverse events and assigning the attribution for each event for all subjects enrolled on the trial. This form must be completed and supplied to Helsinn Healthcare SA within 24 hours/1 business day at the latest on the following working day. The initial report must be as complete as possible, including details of the current illness and (serious) adverse event, and an assessment of the causal relationship between the event and the investigational product(s). Information not available at the time of the initial report (e.g., an end date for the adverse event or laboratory values received after the report) must be documented on a follow-up MDACC SAE reporting form.

Pregnancies and suspected pregnancies (including a positive pregnancy test regardless of age or disease state) of a female subject or the female partner of a male subject occurring while the subject is on study drug, or within 30 days of the subject's last dose of study drug, are considered immediately reportable events. Study drug is to be discontinued immediately in a female patient and the patient instructed to return any unused portion of the study drug to the investigator(s). The pregnancy, suspected pregnancy, or positive pregnancy test must be reported to Helsinn Healthcare SA immediately by phone and facsimile using the MDACC AE report form. The female should be referred to an obstetrician-gynecologist experienced in reproductive toxicity for further evaluation and counseling.

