For toxicity monitoring, we denote the probability of toxicity by $p(T)$, where toxicity is defined as Grade 3-4 clinically relevant non-hematologic toxicity or a serious adverse event that is at least possibly related to the study drug (Common Terminology Criteria for Adverse Events CTCAE version 4.0). We assume as a priori, $p(T) \sim \text{beta}(0.4, 1.6)$. We will stop treating patients if $\text{Pr}(p(T) > 0.20 | \text{data}) > 0.87$. That is, we will stop the trial for new patient enrollment if at any time during the study we determine that there is more than 87% chance that the toxicity rate is more than 20%. The OR rate and the toxicity will be monitored simultaneously using Bayesian stopping boundaries (Table 1) calculated based on beta-binomial distribution. Independence is assumed between OR and toxicity. Patients will be monitored in cohort size of 5, starting from the 5th patient. Multc Lean Desktop (version 2.1) was used to generate the futility/toxicity stopping boundaries and the operating characteristics table (Table 2).

Table 1: Stopping boundaries for OR and toxicity

Number of patients	Stop the trial if	Stop the trial if
--------------------	-------------------	-------------------

evaluated	there are this many OR patients	there are this many patients with toxicities
5	0	3-5
10	0-2	4-10
15	0-4	6-15
20	0-6	7-20

Table 2: Operating characteristics of the Bayesian futility and toxicity monitoring

True OR Rate	True toxicity Rate	Prob (stop the trial early)	Average sample size
0.3	0.1	0.69	15.7
	0.2	0.74	14.6
	0.3	0.84	12.4
	0.4	0.94	9.8
0.4	0.1	0.35	20.3
	0.2	0.46	18.6
	0.3	0.67	15.1
	0.4	0.88	11.3
0.5	0.1	0.13	23.1
	0.2	0.27	21.1
	0.3	0.56	16.8
	0.4	0.83	12.1
0.6	0.1	0.04	24.3
	0.2	0.2	22.1
	0.3	0.52	17.5
	0.4	0.82	12.5

Statistical Analysis Plan

Summary statistics will be provided for continuous variables. Frequency tables will be used to summarize categorical variables. The objective response rate (ORR) will be estimated along with the Bayesian 95% credible interval. Data from all subjects who receive any study drug will be included in the safety analyses. The severity of the toxicities will be graded according to the NCI CTCAE v4.0 whenever possible. We will follow standard reporting guidelines for adverse events. Safety data will be summarized by category, severity and frequency. The proportion of patients with AEs will be estimated, along with the Bayesian 95% credible intervals.

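### The 24-hour request to home physicians covers only life-threatening events, which is narrower than the SAE definition and the monitored toxicity, so other SAEs can reach the investigator late

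*Combined protocol and SAP*

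**What the plan says.** Section 5.6 (Outside Physician Participation During Treatment) allows patients to be followed by a local physician. It sets one timed safety report: "The home physician will be requested to report to the MDACC physician investigator all life threatening events within 24 hours of documented occurrence". The same list asks for other records, including "reports of protocol required laboratory and diagnostic studies and documentation of any hospitalizations", with no time limit. On visits it says: "Patients will return to MDACC each cycle for the first 6 cycles then every 3 cycles as long as on the study for evaluation". Section 5.6 also lists "Continuous assessment of AEs", without saying how this works for a patient in outside care.

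The SAE section (7.2) names death, life threat, hospitalization, incapacity and birth defect as separate outcomes and adds important medical events. IRB reporting is due within 5 working days of knowledge. Under the supplier section (also numbered 7.2), the investigator "will inform Helsinn Healthcare SA of any SAE within 24 hours of being aware of the event".

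Section 8.0 defines the monitored toxicity as "Grade 3-4 clinically relevant non-hematologic toxicity or a serious adverse event that is at least possibly related to the study drug". It is monitored in cohorts of 5, with Table 1 boundaries at 5, 10, 15 and 20 patients and a total of 25.

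**The concern.** The prompt request to the local physician covers one SAE outcome. The stopping rule counts related SAEs of every kind, plus grade 3-4 clinically relevant non-hematologic toxicity. No other clock closes the difference, because the IRB and supplier deadlines both run from the investigator's own knowledge. A local physician could follow the request to the letter and still leave a related hospitalization unreported for some time.

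Two things are at stake. Regulatory and supplier reporting starts late. And a toxicity count taken at a look can be too low, so that enrollment continues past a boundary that has in fact been reached.

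**Working it through.** **1. The passages side by side**

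| Event in local care | Deadline for home physician (5.6) | SAE (7.2) | In toxicity rule (8.0) |
|---|---|---|---|
| Life-threatening | 24 h, requested | yes | if at least possibly related |
| Death | none stated | yes, listed separately | if at least possibly related |
| Hospitalization | records, no deadline | yes | if at least possibly related |
| Incapacity, birth defect, important medical event | none stated | yes | if at least possibly related |
| Grade 3-4 clinically relevant non-hematologic, not serious | none stated | no | yes |

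**2. Intervals between center visits.** Inputs: 28-day cycles and 2-3 patients per month (Section 8.0); visit schedule and a 10-day window either way (Section 5.6); one month = 365.25/12 = 30.44 days.

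- Through cycle 6: 28 days = 0.92 months, during which 1.8-2.8 patients enroll.
- After cycle 6: 3 × 28 = 84 days = 2.76 months, during which 5.5-8.3 patients enroll. With the window this is up to 94 days if one visit shifts, or 104 if both shift apart.
- Spacing of looks: 5/2 months = 10.9 weeks, or 5/3 months = 7.2 weeks.

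These are maximum visit intervals. The plan states no reporting lag.

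**3. The plan's own boundaries.** With a beta(0.4, 1.6) prior, x toxicities in n patients give a beta(0.4 + x, 1.6 + n − x) posterior; stop if Pr(p(T) > 0.20) > 0.87.

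| n | One below boundary | At boundary |
|---|---|---|
| 5 | x=2: 0.778 | x=3: 0.948 |
| 10 | x=3: 0.719 | x=4: 0.895 |
| 15 | x=5: 0.856 | x=6: 0.946 |
| 20 | x=6: 0.826 | x=7: 0.923 |

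This reproduces the toxicity column of Table 1. Exact calculation over the four looks also reproduces all 16 rows of Table 2, within 0.02 on the stopping probability and 0.15 on average sample size. The tables are correct as calculated; they take every toxicity as known at the look. One unknown event changes the decision only when the true count sits exactly on the boundary.

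**4. Which looks the 12-week interval can touch.** Suppose looks follow enrollment (an assumption) and all patients start at cycle 1. At accrual rate r, patient i has been on study (n − i)/r months at look n. Six cycles take 168 days = 5.52 months, so the patient is past cycle 6 if i < n − 5.52r, that is i < n − 11.04 at r = 2 or i < n − 16.56 at r = 3.

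| Look | r = 2 | r = 3 |
|---|---|---|
| 5 | 0 | 0 |
| 10 | 0 | 0 |
| 15 | 3 | 0 |
| 20 | 8 | 3 |

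Section 5.0 credits earlier ruxolitinib (under 3 months) toward the first 3 cycles. If credited time also advances the visit schedule, which the plan does not say, 168 days shrinks toward 84. In the extreme case that every patient has nearly full credit, the condition becomes i < n − 2.76r, giving 1-4 of 10 at the second look and still 0 of 5 at the first.

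If looks instead wait for the 6-cycle response, the look at 10 falls at 10/r + 5.52 months: 10.5 months at r = 2, with 21 enrolled, or 8.9 months at r = 3, when accrual of 25 is complete. Events in cycles 1-6 then arise under 4-weekly visits; only later events in earlier patients face the 12-week interval.

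**5. Sensitivity to incomplete counts.** The share of toxicities known at a look is not in the documents, so it is assumed here. Replace p(T) by share × p(T), with a true response rate of 0.5:

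| Share known | P(stop), p(T) = 0.3 | Average N, p(T) = 0.3 | P(stop), p(T) = 0.4 |
|---|---|---|---|
| 100% (Table 2) | 0.56 | 16.8 | 0.83 |
| 90% | 0.47 | 18.2 | 0.74 |
| 80% | 0.38 | 19.5 | 0.63 |
| 70% | 0.29 | 20.7 | 0.50 |
| 50% | 0.18 | 22.4 | 0.27 |

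This treats an unknown event as unknown at every later look too, so it overstates the effect of mere delay.

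**The case against.** The plan has other contacts. Section 5.1 makes interruption mandatory for drug-related grade 3-4 non-hematologic toxicity, and Section 5.6 requires the center's approval before any dose or schedule change, so such an event should prompt a call. Section 5.2 makes each new pracinostat cycle depend on resolution of drug-related grade 3-4 events. Outside evaluations are documented by telephone, fax or e-mail, and blood counts continue every cycle. Most local physicians would also report a death, whatever the wording. All of this stands, and it makes a full 12 weeks of silence unlikely. None of it sets a deadline for passing on an SAE, however, and a blood count does not reveal non-hematologic events.

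The supplier section exempts some SAEs, such as hospitalization for infection or cytopenia, from expedited reporting. That narrows the effect on the supplier clock, but not on the IRB clock or the toxicity count.

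A reader might infer that SAEs will be up to 12 weeks late throughout, that they will miss the looks, and that 5.5-8.3 extra patients could enroll past the boundary at 10. The documents do not support this. The 84-day interval starts only after cycle 6. If looks follow enrollment and patients start at cycle 1, nobody has reached it at the look at 10. If looks wait for cycle 6, 21-25 of 25 are already enrolled by then, so that many cannot be added. Section 8.0 also words the rule as applying at any time, so a late event is normally delayed rather than lost.

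**Conclusion.** The concern holds as a gap in data flow. The timed request in Section 5.6 is narrower than both the SAE definition in Section 7.2 and the toxicity in Section 8.0, and nothing else in the plan sets a deadline for the remainder. The consequence is late reporting and a possibly delayed toxicity stop; the stop is missed if the decisive event surfaces only after the look at 20.

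The size is modest and cannot be fixed from the documents. The outer limit is the visit interval: about 4 weeks through cycle 6, which includes the first three combination cycles for a patient starting at cycle 1, and about 12 weeks after that. If looks follow enrollment, the longer interval can matter only at 15 patients (0-3 past cycle 6) and 20 patients (3-8 past cycle 6). This rests on steady accrual of 2-3 per month and no credited ruxolitinib time. The loss of stopping probability depends on an assumed share of known events. It would also be wrong to infer that Tables 1 and 2 are in error; they reproduce.

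**What to change.** Reword the Section 5.6 request, and the planned letter to the local physician, so that every event meeting the Section 7.2 SAE definition, expressly including death and any hospitalization, is reported to the investigator within 24 hours of the local physician becoming aware of it. Before each of the four toxicity looks, have the study team confirm, for all treated patients, that no SAE and no monitored grade 3-4 non-hematologic toxicity is outstanding.

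A 24-hour duty on local physicians for every grade 3-4 non-hematologic event, serious or not, is not needed: Section 7 does not ask that of the investigator, and the check before each look covers those events.

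The cost is one reworded sentence, matching text in the letter, a few more local reports and a brief check at four looks. Boundaries, sample size and visit schedule do not change.

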7.0 REGULATORY AND REPORTING REQUIREMENTS

7.1 Adverse Event Reporting for MD Anderson-Sponsored IND Protocols

All adverse events that are possible, probably or definitely related to the study treatment will be captured on the case report form. Any grade 3 or higher adverse event that is considered unrelated or unlikely related to the study treatment will also be recorded. Adverse events will be defined using NCI CTCAE version 4.0.

All adverse events occurring between the time the subject is consented and begins study drug will be considered a baseline event and recorded. Baseline adverse events will be recorded in the case report form in prior medical history. All baseline adverse events that increase in severity during the course of treatment will be captured as an adverse event in the case report form.

Any adverse event that occurs during the study period (up through 30 days after the last day drug is administered) will be followed until clinical recovery is complete and laboratory tests have returned to normal, until progression of the event has been stabilized, or until the PI determines there has been acceptable resolution of the event.

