- Unless otherwise noted, the electronic SAE application (eSAE) will be utilized for safety reporting to and MDACC IRB.
- Serious adverse events will be captured from the time of the first protocol-specific intervention, until 30 days after the last dose of drug, unless the participant withdraws consent. Serious adverse events must be followed until clinical recovery is complete and laboratory tests have returned to baseline, progression of the event has stabilized, or there has been acceptable resolution of the event.
- Additionally, any serious adverse events that occur after the 30 day time period that are related to the study treatment must be reported to the IND Office. This may include the development of a secondary malignancy.

Reporting to FDA:

Serious adverse events will be forwarded to FDA by the IND Sponsor (Safety Project Manager IND Office) according to 21 CFR 312.32. It is the responsibility of the PI and the research team to ensure serious adverse events are reported according to the Code of Federal Regulations, Good Clinical Practices, the protocol guidelines, the sponsor's guidelines, and Institutional Review Board policy.

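### The only scheduled post-treatment adverse-event contact may be made from day 16 and is waived after new MF treatment, so it need not cover the 30-day safety window the plan sets

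*Combined protocol and SAP*

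**What the plan says.** Three places bear on safety follow-up after treatment ends.

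- **Section 5.6 (Evaluation During Study, list on outside physicians).** Site staff are to contact the patient "30 days after discontinuation of protocol +/-14 days to assess for AE's, unless the patient receives further MF-directed treatment". No other post-treatment AE contact is scheduled anywhere in the document.
- **Section 7.1.** The study period for AEs runs "up through 30 days after the last day drug is administered". Starting another MF therapy is not an exception.
- **Section 7.2 (SAE reporting for sponsor IND protocols).** SAEs are captured from the first protocol-specific intervention "until 30 days after the last dose of drug, unless the participant withdraws consent". Related SAEs after that period must also be reported.

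Section 8.0 counts as toxicity a clinically relevant grade 3-4 non-hematologic event, or an SAE at least possibly related to study drug. It states no observation window for either.

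**The concern.** Sections 7.1 and 7.2 say which events are to be captured and until when. Section 5.6 supplies the only scheduled occasion on which the site would ask about them once the patient has stopped. The two do not match in three respects: the earliest permitted day, the waiver, and the date from which days are counted (discontinuation of protocol in one, last dose in the others).

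Toxicity is the trial's secondary objective. The SAP reports the proportion of patients with AEs, and toxicity also drives a stopping rule. The waiver is also tied to why a patient leaves. Lack of therapeutic effect is a removal criterion in Section 5.7, and such patients are plausible candidates for other MF therapy. Any loss of late events could therefore be concentrated in one kind of patient rather than spread evenly.

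**Working it through.** **1. Permitted contact days (inputs: Section 5.6).** Earliest: 30 - 14 = day 16. Latest: 30 + 14 = day 44. Both are counted from discontinuation of protocol.

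**2. Coverage of the 30-day period (inputs: Sections 7.1 and 7.2).** Let L be the number of days from last dose to discontinuation of protocol. The earliest contact then falls on day 16 + L after the last dose, and the longest stretch of the window with no later scheduled contact is max(0, 30 - (16 + L)) = max(0, 14 - L) days.

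| Situation | Days of the 30 with no later scheduled contact |
|---|---|
| L = 0, contact on day 16 | 14 (days 17 to 30; 14/30 = 47%) |
| L = 0, contact on day 30 to 44 | 0 |
| L = 7, earliest contact | 14 - 7 = 7 |
| L of 14 or more, any permitted contact | 0 |
| Waived after further MF-directed treatment | up to 30 |

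A lag is realistic, because Section 5.0 allows a cycle to be delayed by up to 8 weeks. It does nothing for waived patients.

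**3. Other routes by which the site might learn of an event.**

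- Continuous AE assessment is listed in Section 5.6 under evaluation during study.
- Local physicians are asked for hospitalization records and for 24-hour notice of life-threatening events. That list is headed as applying during treatment. The post-treatment contact sentence sits under the same heading, so the heading does not settle the list's scope.
- Even on the wider reading, a grade 3 non-hematologic event managed as an outpatient after the last dose has no assured route to the site.

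**4. The stopping rule itself.** Table 1 follows from the stated prior. Stop for toxicity when 1 - F(0.20; 0.4 + x, 1.6 + n - x) > 0.87, where F is the beta distribution function. At n = 5 this gives 0.778 for x = 2 and 0.948 for x = 3, hence the boundary of 3. All four toxicity boundaries (3, 4, 6 and 7 at n = 5, 10, 15 and 20) reproduce, as do all 16 rows of Table 2. Nothing in the boundaries needs changing.

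**5. Direction of any effect.** The documents give no missed fraction, so m below is an assumption. If a fraction m of patients with toxicity is missed, the rule sees a rate of p(1 - m). With a true response rate of 0.5, the probability of stopping early is:

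| Assumed m | True toxicity 0.30 | True toxicity 0.40 |
|---|---|---|
| 0 (Table 2: 0.56, 0.83) | 0.563 | 0.835 |
| 5% | 0.515 | 0.791 |
| 10% | 0.467 | 0.741 |
| 20% | 0.375 | 0.625 |
| 30% | 0.294 | 0.499 |

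The table shows direction only. It applies only if post-treatment events count toward the rule, which Section 8.0 leaves open, and it treats the loss as present at every look.

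**The case against.** The best case for the plan is that the duty to capture events does not depend on this contact. Section 7.2 requires SAE capture to 30 days for everyone who has not withdrawn consent, including patients whose contact is waived, and related SAEs remain reportable afterwards. Sections 7.1 and 7.2 also require events to be followed to recovery or stabilization, so a patient who leaves with an open event is not lost. The nominal contact is on day 30, and any contact from then to day 44 covers the whole period. The waiver has a reason too: new MF therapy confounds attribution.

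Most of this stands, and it limits the point to events that first arise after the last dose and do not otherwise reach the site. It does not remove the mismatch, because a duty to record is of little use without an occasion to ask. Difficulty of attribution is a reason to record when the new therapy began, not to stop asking about events that Section 7.2 still requires.

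Four stronger readings are tempting, and the documents do not support them.

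- *The contact cannot cover the window.* It can: days 30 to 44 are permitted, and a lag between last dose and discontinuation narrows the gap. It need not cover it.
- *Toxicity will be under-counted.* This is not shown. Events on treatment are assessed continuously, and SAE duties continue after it.
- *The size can be read from the earlier pracinostat MF study in Section 2.3, where 9 + 6 = 15 of 22 patients left for lack of response or progression.* Those are reasons for leaving a single-agent study. They do not say how many started another therapy within 30 days, which is what triggers the waiver.
- *One missed event would reverse a stopping decision.* That is true of any count lying at a boundary and says nothing about how likely it is. The rule counts patients, so a late event matters only in a patient with no earlier qualifying toxicity, and only if it arises before a look. With treatment intended for at least 6 months and accrual of 2-3 patients a month, relatively few patients may have left by the early looks.

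**Conclusion.** The point holds as an inconsistency in safety ascertainment that should be fixed. It is not an error in the design or in the stopping boundaries. A site in full compliance with Section 5.6 can leave unasked-about up to 14 days of the 30-day window for a contacted patient, and up to 30 days for an exempt one. The 14-day figure assumes that discontinuation coincides with the last dose and that the call is made on the earliest permitted day.

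How many events would be missed cannot be derived from the documents. Any effect would make the combination look safer than it is, and would fall more on patients who leave for other MF therapy. Whether it could reach the stopping rule depends on an observation window that Section 8.0 does not state.

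**What to change.** Reconcile Section 5.6 with Sections 7.1 and 7.2:

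1. Count the contact from the last dose of study drug, not from discontinuation of protocol.
2. Set it at day 30 with a window of 0/+14 days, and ask about events through day 30.
3. Make it for every patient who has not withdrawn consent, including those starting other MF treatment.
4. Record the start date of that treatment, so that later events can be shown separately.
5. In Section 8.0, state whether events in the 30 days after the last dose count toward the toxicity stopping rule.

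With these changes, the stretch of the window with no later scheduled contact falls from up to 14 days, or up to 30 for exempt patients, to 0. The cost is a short amendment to Section 5.6, a clarifying sentence in Section 8.0, and one extra call for each patient now exempt. Some events after a switch of therapy will be harder to attribute. Sample size and stopping boundaries do not change.
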